9.2 Sample Size Determination

Approximately 350 eligible participants will be randomly assigned to double-blind treatment with one of 4 dose levels of MEDI7352 or placebo. Recruitment will continue until the planned unconditional power of the study is achieved (ie, when statistical information equivalent to 255 participants completing the treatment period is reached or approximately 350 randomised participants, whichever is sooner. The statistical information will be calculated based upon ongoing blinded study data. Further details will be given in the Statistical Analysis Plan.

With statistical information equivalent to 255 evaluable participants, the study will have greater than 90% power to detect a statistically significant (at overall 1-sided $\alpha = 0.025$) dose-response relationship using a MCP-Mod approach for the primary endpoint: Change in the weekly average of daily NRS pain scores from baseline to Week 12. This assumes that the true Week 12 placebo-corrected change from baseline difference at the CCI dose is 1.5, the true dose-response follows a maximum response (Emax) relationship with a dose that produces half of the E_{max} (ED₅₀) = CCI and a SD = 2.4.

The 6 candidate dose response models incorporated into the MCP-Mod test were chosen to reflect potential convex, linear, and concave dose-response relationships and are as follows:

- \forall Three convex E_{max} models with increasing ED₅₀: ^{CCI}
- \forall One model linear in dose
- \forall Two concave exponential models defined by 10% and 25% of the maximum drug effect at CCI

The above calculations were performed using the software R and the R-package 'DoseFinding' [https://cran.r-project.org/web/packages/DoseFinding/DoseFinding.pdf]

9.3 **Populations for Analyses**

The following populations are defined (Table 9):

Population/Analysis set	Description
Screening set	This set includes all participants who provide informed consent and/or assent and provide demographic and/or baseline screening assessments, regardless of the participant's randomisation and treatment status in the study.

Table 9Populations for Analysis

Population/Analysis set	Description
Full analysis set	This set will be used for all efficacy analyses, and it is defined according to the intent-to-treat principle as including all randomised participants.
PK set	This set includes all participants who received at least one dose of double- blind IP per the protocol for whom any postbaseline PK data are available and who do not violate or deviate from the protocol in ways that would significantly affect the PK analyses.
Safety set	This set will include all participants who receive at least one dose of double- blind IP

Table 9Populations for Analysis

IP, investigational product; PK, pharmacokinetics

9.4 Statistical Analyses

The SAP will be finalised before the first interim analysis and will include a more technical and detailed description of the statistical analyses described in this section. This section is a summary of the planned statistical analyses of the most important endpoints including primary and key secondary endpoints.

9.4.1 General Considerations

Formal statistical analysis will be undertaken for the primary and key secondary efficacy endpoints, with the aim of maintaining overall family-wise type-1 error at 5% level (2-sided) or, equivalently, at 2.5% level (1-sided). The analysis of any remaining endpoints (including other efficacy, safety, and those in Section 9.4.4) will be for estimation purposes.

Generally, for each endpoint, baseline is defined as the latest assessment prior to the first dose of randomised treatment. For the primary endpoint (change in weekly average of daily NRS pain scores), the baseline is defined as the mean of daily NRS pain scores recorded during the 7-day period immediately prior to randomisation, ie, Day -7 to Day -1, inclusive. Details of 'analysis visit windows' used for statistical reporting will be included in the SAP.

9.4.2 Efficacy

All efficacy variables will be summarised descriptively including number of observations, mean, SD, minimum, median, and maximum for continuous variables, and frequency of observations in each category and percentage for categorical variables. Primary and secondary endpoint efficacy data will be tabulated according to the 'observed cases' approach. In addition, if there is missing or unevaluable data at a key analysis time-point (Weeks 4, 8, and 12) then results will also be tabulated according to single imputation 'last-observation-carried forward' (LOCF) or 'baseline-observation-carried-forward' (BOCF), depending upon the intercurrent event leading to missing or unevaluable data. The presentation of single

imputed data is intended as an approximation to the approach taken for the formal analyses and also to allow historical comparison.

9.4.2.1 Primary Endpoint

An 'attributable 4' estimand strategy will be adopted for primary endpoint data missing or affected by any of the following 4 intercurrent events:

- \forall Discontinuation due to lack of efficacy, or an AE
- \forall Discontinuation due to other reasons such as loss to FU or external circumstances
- ∀ Taking prohibited pain medication during the treatment period that may confound the effect of initially randomised treatment on the primary endpoint
- ∀ Taking excessive permitted rescue medication that may confound the effect of initially randomised treatment on the primary endpoint

The rationale for choosing the attributable estimand (Darken et al 2020) is because if a participant does not receive treatment for the duration of the study (due to an AE or lack of efficacy), or switches to a prohibited therapy, or uses excessive rescue medication, he/she is considered to be a treatment failure and so handled with a composite estimand strategy, while a hypothetical estimand strategy is used for intercurrent events not considered to be related to randomised treatment such as discontinuation due to 'other reasons'.

Note that it is expected that participants would be switched to alternative treatments following discontinuation of randomised treatment or withdrawal, which would confound any assessment of efficacy attributable to randomised treatment; therefore, retrieved dropout information will not be collected.

Primary endpoint data missing due to discontinuation due to lack of efficacy or an AE will be imputed assuming an unfavourable outcome. Data affected by prohibited or excessive rescue medication will be set to missing and imputed assuming an unfavourable outcome. For these intercurrent events, a return-to-baseline multiple imputation approach will be used which assumes that any treatment effects observed prior to the intercurrent event are washed out, such that the mean effect at the end of the study among such participants is the same as that at baseline. This seems reasonable where participants enter the study with a chronic level of moderate-to-severe pain and the treatment effect is expected to be reversible.

Primary endpoint data missing due to other reasons will be imputed using a "missing-atrandom" multiple imputation approach.

Further details of the multiple imputation models and number of imputations will be included in the SAP.

The main statistical analysis of the primary efficacy endpoint at Week 12 will use the MCP-Mod approach, which is a well-established statistical methodology for establishing both the existence of a dose response and modelling the underlying dose-response relationship (EMA 2013, FDA 2015).

There are 2 steps to MCP-Mod:

- ∀ The 'MCP' step is a rigorous method to establish presence of a dose response while protecting the type 1 error and, if the dose-response relationship is statistically significant, then
- \forall The 'Mod' step estimates the dose response function and associated model parameters, such as ED₅₀ in the case of E_{max} relationship.

The MCP test will use linear contrasts corresponding to the 6 candidate models described in Section 9.2. The underlying model will be an analysis of covariance (ANCOVA) with dependent variable 'change from baseline to Week 12', and independent variables will include dose, 'baseline score' and KL grade. The random error is assumed to be normally and independently distributed with constant variance.

If the MCP test is statistically significant, then the Mod step will select the most appropriate dose-response model (including the same covariates as the ANCOVA model) from which various estimates will be derived (together with confidence intervals) of parameters of interest such as ED_{50} , 90% of the E_{max} (ED_{90}), dose to achieve selected target effects, and model estimates of the treatment effect at doses studied.

Pairwise testing will be performed using the multiple comparison approach described in Section 9.1 based upon the same ANCOVA model as used for the MCP-Mod analyses.

For each analysis, the testing and estimation will be based upon Rubin's method of combination of the repeated analyses of complete multiply-imputed datasets.

9.4.2.2 Secondary Endpoint(s)

The same analysis approach as for the primary endpoints will be applied to the analysis of the key secondary endpoints WOMAC pain, WOMAC physical function, and PGA of OA.

Other continuous secondary endpoints will be analysed by single BOCF/LOCF imputation approaches, where LOCF is used for intercurrent event discontinuation due to other reasons and BOCF for other intercurrent events.

For binary (responder-type) secondary endpoints, a logistic regression analysis will be performed with the same covariates as for the respective continuous endpoint. A mixed BOCF/LOCF imputation will be used for missing or unevaluable data. In this analysis, LOCF would be used to assign response for participants with intercurrent event discontinuation due to other reasons and BOCF imputation (ie, a participant would be a nonresponder) otherwise.

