To assess the efficacy of MEDI7352	Key secondary endpoints:
compared to placebo on additional measures of efficacy in participants with painful OA	Change in the WOMAC pain subscale from baseline to Week 12
of the knee	 Change in the WOMAC physical function subscale from baseline to Week 12 Change in the PGA of OA from baseline to Week 12
	Other secondary endpoints:
	 Change in the WOMAC pain subscale from baseline to Weeks 2, 4, 6, 8, 10, and 18
	• Change in the WOMAC physical function subscale from baseline to Weeks 2, 4, 6, 8, 10, and 18
	• Change in the WOMAC overall scores from baseline to Weeks 2, 4, 6, 8, 10, 12, and 18
	• Change in the WOMAC stiffness scores from baseline to Weeks 2, 4, 6, 8, 10, 12, and 18
	• Change in PGA of OA from baseline to Weeks 2, 4, 8, 10, and 18
	• Percentage of responders as measured by the OARSI responder index using the OMERACT-OARSI definition (Pham et al 2004) at Weeks 2, 4, 8, 12, and 18
	 Percentage of participants who have achieved an improvement of ≥ 2 points in PGA of OA at Weeks 2, 4, 8, 12, and 18
	• Change in the weekly average of daily NRS pain scores from baseline to Weeks 2, 4, 6, 8, 10, and 18
	• Percentage of participants who have achieved ≥ 30% and ≥ 50% reductions in the weekly average of daily NRS pain scores from baseline to Weeks 2, 4, 8, 12, and 18
	 Percentage of participants who have achieved ≥ 30% and ≥ 50% reductions in WOMAC pain subscale scores at Weeks 2, 4, 8, 12, and 18
	 Percentage of participants who have achieved ≥ 30% and ≥ 50% reductions in WOMAC physical function subscale at Weeks 2, 4, 8, 12, and 18
To assess the PK of MEDI7352 in participants with painful OA of the knee	Serum concentration of MEDI7352

Objectives	Estimands descriptions/endpoints
To assess immunogenicity of MEDI7352 in participants with painful OA of the knee	Presence of ADA to MEDI7352ADA titre
Safety objectives	

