	• Percentage of responders as measured by the OARSI responder index using the OMERACT-OARSI definition (Pham et al 2004) at Weeks 2, 4, 8, 12, and 18			
	 Percentage of participants who have achieved an improvement of ≥ 2 points in PGA of OA at Weeks 2, 4, 8, 12, and 18 			
	• Change in the weekly average of daily NRS pain scores from baseline to Weeks 2, 4, 6, 8, 10, and 18			
	• Percentage of participants who have achieved $\geq 30\%$ and $\geq 50\%$ reductions in the weekly average of daily NRS pain scores from baseline to Weeks 2, 4, 8, 12, and 18			
	• Percentage of participants who have achieved ≥ 30% and ≥ 50%, reductions in WOMAC pain subscale scores at Weeks 2, 4, 8, 12, and 18.			
	• Percentage of participants who have achieved ≥ 30% and ≥ 50% reductions in WOMAC physical function subscale at Weeks 2, 4, 8, 12, and 18			
To assess the PK of MEDI7352 in participants with painful OA of the knee	Serum concentration of MEDI7352			
To assess immunogenicity of MEDI7352 in	• Presence of ADA to MEDI7352			
participants with painful OA of the knee	ADA titre			
Safety objectives				
To assess the safety and tolerability of MEDI7352 compared with placebo in participants with painful OA of the knee	Safety and tolerability will be evaluated based on AEs, vital signs, and clinical laboratory assessments including but not limited to:			
	AEs and SAEs			
	Physical examinations			
	Neurological examinations Tatal Neurorethy Score nume			
	Total Neuropathy Score-nurseWeight			
	WeightVital signs (supine and standing BP, pulse rate,			
	temperature, respiratory rate)			
	Survey of Autonomic Symptoms12-lead ECGs			

Table 2Primary and Secondary Objectives

Objectives	Estimands descriptions/endpoints
	Clinical laboratory testing (haematology, chemistry, coagulation, and urinalysis)
	CRP (inflammatory biomarker)
	Concomitant medications and therapies
	Injection site reactions
	X-ray or/and MRI of large joints ^a

Table 2Primary and Secondary Objectives

^b During the treatment period, participants can receive the ABPM device at any of the study visits between Weeks 8 and 12 (inclusive).

ABPM, ambulatory blood pressure monitoring; ADAs, antidrug antibodies; AE(s), adverse event(s); BP, blood pressure; CRP, C-reactive protein; CCI ; CCI

 CCI
 ; ECGs, electrocardiograms;
 ; NGF, nerve

 growth factor; PGA, Patient's Global Assessment; MRI, magnetic resonance imaging;
 ; NGF, nerve

 CCI
 ; NRS, numerical rating scale; OA, osteoarthritis; OMERACT-OARSI, Outcome

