Participants who discontinue IP early will be asked to complete study assessments at the ET visit (ie, Week 12 assessments) as soon as possible and then to enter the FU period.

Participants who discontinue IP prematurely may be given standard-of-care therapy for their pain after the ET visit as deemed appropriate by the investigator and in alignment with local guidelines/label (including paracetamol, aspirin, NSAIDs, and COX-2 inhibitors if deemed necessary). However, initiation of NSAIDs, COX-2 inhibitors, and aspirin (in doses that exceed 325 mg/day) is prohibited until after 5 half-lives following the last IP administration (ie, approximately 3 weeks). Note that it is recommended to postpone NSAIDs/COX-2 inhibitors intake until 8 weeks after the last IP administration. In addition, initiation of corticosteroid therapy (eg, intra-articular injections) should be deferred until at **least 8 weeks** after the last IP administration.

Refer to the SoA (Table 1) for assessments to be performed at the ET visit and FU period. All participants prematurely discontinued from IP are expected to complete the ET visit and the 24-week FU period, which consists of 3 FU clinic visits and 4 phone calls at the times indicated below:

- ∀ ET visit: Week 12 assessments to be performed as soon as possible after the last IP administration. The following assessments/procedures will not be performed beyond the ET visit:
 - # Daily NRS pain score
 - # DSIS
 - # Rescue medication recording
 - # WOMAC
 - # PGA
 - # Blood collection for PK, ADA, and PD biomarkers
- ∀ FU phone call 1: To be conducted 5 weeks after the last IP administration
- ∀ FU visit 1: Week 18 assessments to be performed 8 weeks after the last IP administration
- ∀ FU phone call 2: To be conducted 11 weeks after the last IP administration
- ∀ FU phone call 3: To be conducted 14 weeks after the after the last IP administration
- ∀ FU phone call 4: To be conducted 18 weeks after the last IP administration
- ∀ FU visit 2: Week 32 assessments to be performed 22 weeks after the last IP administration
- ∀ FU visit 3: Week 36 assessments to be performed 26 weeks after the last IP administration

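### LOCF for 'other reasons' discontinuers puts generally on-treatment scores into the off-drug Week 18 secondary estimates, and departs from the primary's multiple imputation for the Week 12 NRS responder analyses

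*Protocol*

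**What the plan says.** Section 9.4.2.2 of the protocol sets three rules.

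- Key secondary endpoints (Week 12 WOMAC pain, WOMAC physical function and PGA): "The same analysis approach as for the primary endpoints will be applied to the analysis of the key secondary endpoints". That means multiple imputation.
- Remaining continuous secondary endpoints: "Other continuous secondary endpoints will be analysed by single BOCF/LOCF imputation approaches, where LOCF is used for intercurrent event discontinuation due to other reasons". BOCF covers the other intercurrent events.
- Responder endpoints: "LOCF would be used to assign response for participants with intercurrent event discontinuation due to other reasons". The other intercurrent events count as nonresponse.

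Section 3 and the Synopsis place Week 18 among these endpoints. The continuous NRS endpoint is "Change in the weekly average of daily NRS pain scores from baseline to Weeks 2, 4, 6, 8, 10, and 18". The NRS responder endpoint (at least 30% and at least 50%) concerns "reductions in the weekly average of daily NRS pain scores from baseline to Weeks 2, 4, 8, 12, and 18".

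For early discontinuers, Section 7.1.2 says: "The following assessments/procedures will not be performed beyond the ET visit". The list that follows includes the daily NRS, WOMAC and PGA. Section 9.3 puts every randomised participant in every efficacy analysis.

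For the primary endpoint, Section 9.4.2.1 says "a hypothetical estimand strategy is used for intercurrent events not considered to be related to randomised treatment", with missing-at-random multiple imputation. It justifies return-to-baseline imputation for treatment failures as reasonable "where participants enter the study with a chronic level of moderate-to-severe pain and the treatment effect is expected to be reversible".

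**The concern.** Week 18 is the time point that shows whether pain relief lasts once drug has gone. An early discontinuer has no observed Week 18 score by design, so the imputation rule decides the value. For someone who stopped for other reasons, the rule supplies a score from the treatment period or the ET visit. In an active arm that score generally still contains drug effect. In the placebo arm it contains none. The between-arm difference at Week 18 is therefore pulled towards the on-treatment difference, and more so in arms with a larger on-treatment effect. In a dose-response trial this could look like persistence, or like a dose response in persistence.

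At Week 12 the issue is one of target. The same missing weekly NRS mean is filled by missing-at-random multiple imputation in the primary analysis and by LOCF in the responder analyses. LOCF does not estimate what would have happened had the participant continued, which is the primary's hypothetical strategy, and it treats the filled value as known.

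**Working it through.** **The plan's own figure.** The protocol gives no figure for this rule. The nearest is the primary's power, stated as above 90% with a difference of 1.5 at one redacted dose and SD 2.4. With 51 per arm, IV-equivalent dose spacing 15:50:150:300, the 1.5 placed at the top dose and assumed values for the redacted parameters, simulation gives 91.8% to 94.6%. That agrees with the statement. Only the 1.5 and the 2.4 are borrowed below.

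**Is Week 18 off drug?** Section 7.1.2 equates five half-lives with about 3 weeks, so one half-life is 21/5 = 4.2 days. The last dose is at Week 10.

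- Week 12: 14/4.2 = 3.3 half-lives, leaving about 10%.
- Week 18: 56/4.2 = 13.3 half-lives, leaving about 0.01%.

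On the protocol's own figure, drug is essentially gone at Week 18 but not at Week 12.

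**Size of the Week 18 bias.** Let p be the share carried forward by LOCF, w the fraction of the effect washed out by Week 18, and d the arm's effect in the carried score. The spurious difference in favour of drug is

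bias = p × w × d.

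None of the three is stated for this purpose, so they are assumed: p from 5% to 15%; w = 1; d from 0.75 (half the design effect) to 1.5 (all of it).

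| p | d = 0.75 | d = 1.5 |
|---|---|---|
| 5% | 0.0375 | 0.075 |
| 10% | 0.075 | 0.15 |
| 15% | 0.1125 | 0.225 |

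The range is about 0.04 to 0.23 NRS points. With half washout (w = 0.5) every entry halves.

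For scale, with 350 randomised equally to five arms there are 70 per arm. The standard error of a difference is then √(2 × 2.4²/70) = 0.41, so the bias is about 0.1 to 0.55 standard errors.

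**Check by simulation** (4,000 two-arm trials, 70 per arm, no true effect left at Week 18, d = 1.5; assumed baseline mean 7 and SD 1.3, placebo change −2, correlation 0.7 between on- and off-treatment change):

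| p | Spurious difference favouring drug | Bias in ≥30% responder difference | One-sided nominal 2.5% rejections |
|---|---|---|---|
| 0% | none (0.01 the other way) | 0 points | 2.9% |
| 5% | 0.07 | about 1 point | 4.0% |
| 10% | 0.16 | about 2 points | 6.1% |
| 15% | 0.22 | about 4 points | 8.7% |

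The differences match the formula. The last column is only a gauge of how far an interval would be off-centre, because no formal test is planned for these endpoints.

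**Week 12, side by side.** The event (discontinuation for other reasons), the variable (weekly NRS mean) and the visit are the same. Section 9.4.2.1 uses missing-at-random multiple imputation with Rubin's combination. Section 9.4.2.2 uses one carried-forward score, classified as response or nonresponse, in a logistic regression. The sensitivity analyses in Section 9.4.6 cover only the primary and key secondary endpoints, so none is specified for the responder result. No size is attached here, because it depends on when participants leave and on their trajectory.

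**The case against.** The strongest reply is that nothing decisional is touched. Section 9.4.1 confines formal analysis to the primary and key secondary endpoints and makes the rest estimation only. The key secondaries already use the primary's method. That stands, and it limits the weight of the point. It does not excuse an estimate biased in a known direction, and the method is fixed in the protocol rather than left open.

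Several stronger readings are tempting, but the documents do not support them.

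- *Single imputation as a whole carries on-drug scores.* Only the LOCF branch does. BOCF uses the pre-treatment baseline, in line with the primary's return-to-baseline assumption.
- *Every such discontinuer contributes an on-drug score.* Placebo participants do not, and the full analysis set may include undosed people. Section 7.1.3 allows a hold of up to 28 days before permanent discontinuation; 28/4.2 = 6.7 half-lives, so some ET scores may already be largely off drug.
- *The protocol contradicts itself.* The difference in method between tiers is openly stated and keeps the same split of intercurrent events. It is a methodological inconsistency, not a textual conflict.
- *The drop-out share can be read from the sample size.* A 15% loss follows only from the superseded target of 300. The 27% from 1 − 255/350 is a ceiling: recruitment may stop earlier, and 255 refers to statistical information, not a count of completers. The split by reason is unknown. COVID-19 discontinuations recorded as adverse events would go to BOCF.
- *The full 1.5 sits in every carried score.* It is assumed at one dose only, lower doses would carry less under the assumed Emax shape, and people who leave early may have accrued only part of it. Hence the lower value of 0.75.

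It is also fair to say that drug half-life is not duration of pain relief. The protocol calls the effect reversible but gives no time course, so full washout remains an assumption.

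**Conclusion.** The point holds in a limited form. For discontinuers for other reasons, LOCF is a poor fill for the post-treatment Week 18 value and biases the Week 18 estimates towards persistence of effect. The size is about 0.04 to 0.23 NRS points if 5–15% are carried forward, the effect has fully washed out and the carried score holds 0.75 to 1.5 points of effect. It is smaller with partial washout, and it varies by arm. At Week 12, the NRS responder analyses do not target the primary's hypothetical strategy and carry no imputation uncertainty.

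A reader might infer from the rejection rates above that the trial's type I error is inflated. It is not: these endpoints lie outside the alpha-controlled family, and the primary and key secondary results, the power and the alpha are unaffected.

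**What to change.** In Section 9.4.2.2:

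1. For discontinuation for other reasons, derive the other continuous secondary values and responder status from the primary's missing-at-random multiple imputation. Classify response within each imputed dataset and pool by Rubin's method. Keep return-to-baseline or nonresponse for the other intercurrent events.
2. For Week 18, either extend the imputation using completers' off-drug Week 18 data, or restrict Week 18 to treatment completers, as Section 8.1.9 already does for rescue medication. If restricted, say plainly that the estimate applies to completers.
3. Keep the BOCF/LOCF results as supportive tabulations, consistent with Section 9.4.2, which presents single imputation as an approximation to the formal analyses and an aid to historical comparison.

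The cost is a wording change and a little more analysis work. No new data are needed.
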